**Table 1: Selection Criteria**

Inclusion Criteria	I1. At least 18 years old; I2. Injury within 72 hours at the time of consent; I3. Head injury requiring hospital admission;; I4. A Glasgow Coma Scale (GCS) score of 9-12 or 13-15 with abnormal imaging.
Exclusion Criteria	E1. Need for emergency neurosurgical intervention (including placement of intracranial pressure monitoring devices or drainage catheters); E2. Hemodynamic instability as determined by the clinician; E3. History of any of the following: (i) brain tumor; (ii) prior TBI occurring within the past year and requiring hospital admission; (iii) a new diagnosis within the past year of either stroke or epilepsy; (iv) an established diagnosis of any of the following neurodegenerative diseases: Alzheimer’s, Picks, Parkinson’s, Lewy body dementia, Huntington’s, amyotropic lateral sclerosis, spinocerebellar ataxia, vascular dementia, HIZ-associated dementia, dementia due to metabolic causes (Addison, Cushing, hypothyroidism, renal failure, prophyrias, Wilson, mitochondrial diseases, Wernicke-Korsakoff syndrome, and dementia of unknown etiology. E4. Pregnancy (all women of child-bearing age will need to have a negative urine pregnancy test prior to the start of the interventional portion of the study); E5. Electrical implants such as cardiac pacemakers or perfusion pumps; E6. Ferromagnetic implants such as aneurysm clips, surgical clips, prostheses, artificial hearts, valves with steel parts, metal fragments,

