## **9. Statistical Methods**

In this pilot study, the study size is limited by number of recruitable patients admitted to MGH emergency department. Based on prior-year admission records, the itemized inclusion/exclusion criteria, and an assumed 80% consent rate, we estimate an average enrollment of 1 patient per week.

The sufficiency of these enrollments toward powering the primary hypothesis (DTI outcome measure) is presented below. These calculations require an assumption of the acute LLLT therapeutic effect size, which is unknown and cannot reasonably be estimated from either the preclinical data or the clinical stroke studies. Our analysis is based on an assumed effect size of 25%.

The coefficient of variation for fractional anisotropy (FA) is based on data from a cohort of 12 mild to moderate TBI patients scanned using quantitative MRI [30]. For this cohort, FA was measured in 16 regions of the brain. The coefficient of variation (CV), defined as the ratio of mean to the standard deviation, was 53.45%. However, this study included mild to moderate. With the more narrow inclusion of moderate TBI, we estimate a FA CV of 40% (based on clinical and research experience of the investigators, and knowing that the CV for healthy volunteers is 25%). The required sample size for detecting changes in FA associated with acute LLLT [31] is then 82 (41 patients in each group). We note that other diffusion parameters (mean diffusivity, axial diffusivity, and radial diffusivity) featured much lower CV, and would be sufficiently powered with this sample size.

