Light Therapy for Moderate Traumatic Brain Injury

NCT02233413

Statistical Analysis

6.26.20

Statistical Analysis

All statistical analyses were performed using R Language for Statistical Computing (version 3.6.0). Differences and relations were considered statistically significant at $p < 0.05$. All results are presented as mean + standard deviation (S.D.) unless noted otherwise. Baseline differences across groups were compared via using one-way ANOVA for continuous variables (e.g., Age, RPQ scores) and via Chi-Square test for categorical variables. To test neuroreactivity of LLLT via its effect on the diffusion tensor parameters, we used a linear mixed effect (LME) model with treatment (light therapy vs. sham) and time point (acute, early sub-acute, late sub-acute) as fixed effects, and tract and time point nested within each patient as random effects. All patients with at least one MRI were included in this analysis. Conformity of the data to statistical assumptions were checked by investigating QQ plots of the data. LME models, which are akin to multiple regression models that can account for correlations due to repeated measures, have several advantages in this context. LME modeling allowed us to pool all our data --- i.e., across treatment groups and three time points, as well as across all 18 tracts --- to examine relationships robustly. Moreover, because the LME model allows partially repeated measures, it can accommodate data from subjects with missing timepoints (e.g., missing MRI sequences). In addition, the LME model treats each timepoint as a separate variable. Therefore, any baseline difference in DTI parameters across the LLLT and sham groups did not confound the overall analysis enabling one to robustly identify differences in DTI parameters across the treatment groups while explicitly accounting for repeated measurements, within-tract and within-subject correlations, and missing time points.

A similar LME model (treatment group and time point as fixed effects, and patient as a random effect) was used to test for the effect of LLLT on clinical symptoms). The p values for the fixed effects in the LME model were calculated using type III analysis of variance table with Satterthwaite's degrees of freedom method.

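### The DTI model adjusts for neither entry GCS nor age, so it gives up some precision and leaves chance imbalance uncorrected

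*SAP*

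**What the plan says.** The SAP's DTI model takes "treatment (light therapy vs. sham) and time point (acute, early sub-acute, late sub-acute) as fixed effects", with tract and time point nested within patient as random effects. Age appears in the SAP only as an example of a variable compared between groups at baseline. GCS is not mentioned there.

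Section 9 of the protocol ties the sample size to this outcome: "The sufficiency of these enrollments toward powering the primary hypothesis (DTI outcome measure) is presented below". It assumes a 25% effect. The cited cohort's CV for fractional anisotropy (FA) "was 53.45%. However, this study included mild to moderate", and section 9 then lowers it: "With the more narrow inclusion of moderate TBI, we estimate a FA CV of 40" per cent. The result is 82 subjects, 41 per group.

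On design, three places matter:
- Table 1 (I1, I4) admits adults of any age from 18 with "A Glasgow Coma Scale (GCS) score of 9-12 or 13-15 with abnormal imaging".
- Section 7 randomises 1:1 within sequential groups of ten and names no stratification factor.
- Section 7.2 places the baseline MRI after the first helmet application.

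**The concern.** The only treatment term the SAP lists is the main effect. That is a between-patient comparison in at most 90 subjects. Patient-level random effects describe the correlation of repeated scans and tracts, but they do not take between-patient variance out of the error of that comparison. A pre-treatment variable that predicts FA would do so if entered as a fixed effect.

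The usual covariate, a pre-treatment value of the outcome, does not exist here because no scan precedes the first application. Entry GCS and age are therefore among the few pre-treatment predictors available. Section 9's own reason for lowering the CV is that a narrower severity range varies less, so the plan treats severity as relevant to FA. Yet severity is balanced neither by stratification nor by the model. What is at stake is a wider standard error than necessary, and a treatment estimate that carries any chance imbalance in severity or age.

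**Working it through.** **Inputs.** Effect 25%, CV 40% and 41 per arm are from section 9. The significance level of 0.05 is from the SAP; two-sided testing is assumed because sidedness is not stated. Section 9 states no power; 80% is assumed because it reproduces the plan's number. R² for GCS and age is not given in the documents and is assumed to lie between 0.05 and 0.30.

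**1. Reproduce the plan's sample size.** n per arm = 16 × (CV / effect)² = 16 × (0.40 / 0.25)² = 16 × 2.56 = 40.96, rounded up to 41, or 82 in total. This matches section 9.

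**2. Power without covariates.** Standardised effect d = 0.25 / 0.40 = 0.625. The noncentral t with 41 per arm and 80 degrees of freedom gives 79.8%.

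**3. Power with covariates.** Residual CV = 0.40 × √(1 − s × R²). Here s is the share of the variance that lies between patients, and R² is the fraction of that share explained by GCS and age. Two degrees of freedom are spent, leaving 78.

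| R² | s = 1 | s = 0.5 | s = 0.25 |
|---|---|---|---|
| 0 | 79.8% | 79.8% | 79.8% |
| 0.05 | 81.8% | 80.8% | 80.3% |
| 0.10 | 83.8% | 81.8% | 80.8% |
| 0.20 | 87.8% | 83.8% | 81.8% |
| 0.30 | 91.6% | 85.8% | 82.8% |

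The gain is about 2 to 12 points if all the variance is between patients, about 1 to 6 if half is, and about 0.5 to 3 if a quarter is. The share s is left open because section 9's source CV comes from 12 patients measured in 16 regions, and the text does not say whether it mixes regional and between-patient variation. The model's tract effect would already absorb a regional part.

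**4. Cost if the covariates predict nothing.** At R² = 0, power moves from 79.83% to 79.81%, a loss of 0.02 points.

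**5. What section 9's two CVs imply.** 1 − (40 / 53.45)² = 0.44, so moving from the source cohort to the assumed trial population removes 44% of the variance. That reduction is already inside the 40% that produces 82 subjects. If the narrowing did not happen and the CV stayed at 53.45%, unadjusted power at 41 per arm would be 55.3%. Explaining 44% of that variance would only bring power back to 79.8%.

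**The case against.** The strongest case against is that leaving out covariates is not an error. Allocation is randomised 1:1, so the unadjusted comparison is valid. The trial is also a pilot whose synopsis names safety and feasibility as the primary endpoint. That stands, and it limits the point to efficiency and chance imbalance. A reader might infer that the DTI result would be biased by design; the documents do not support that.

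A reader might also apply the 44% on top of the 40% CV, which would give 96.2% power and a gain of 16 points. This counts the same variance twice, as step 5 shows. Section 9 compares CVs across populations, partly on investigators' judgement. It gives no share of FA variance explained by GCS within the enrolled range.

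Nothing in the documents links age to FA. That also stands: section 9's reasoning supports GCS, and age is included as ordinary prognostic adjustment.

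If the intended contrast were treatment by time, patient-level random effects would already remove most of what stable covariates explain. The SAP lists no such term, so this does not remove the point.

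Finally, the SAP is dated 6.26.20 and written in the past tense, so adjustment may no longer be possible before unblinding. That affects how the adjusted model should be labelled, not whether it is informative.

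**Conclusion.** The point holds as a near-costless improvement, not as a flaw in validity. The DTI model omits two pre-treatment variables that every subject has, in a design with no stated stratification by either and no pre-treatment scan.

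The gain cannot be derived from the documents. With an assumed R² of 0.05 to 0.30, CV 40% and 41 per arm, power rises from 79.8% to between 81.8% and 91.6% if all the variance is between patients. If half or less is, the gain is at most about 6 points. These figures treat FA as a single summary per subject, which is a simplification of the 18-tract model. They apply to the treatment main effect. The case for GCS is stronger than the case for age.

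**What to change.** In the SAP, add entry GCS (the score, or 9-12 against 13-15) and age as fixed effects in the DTI mixed model for each diffusion parameter. Specify this before unblinding, and report the unadjusted model as a sensitivity analysis. If unblinding has already occurred, keep the unadjusted model as the main analysis and report the adjusted one as a labelled sensitivity analysis.

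The cost is one line of SAP wording and two degrees of freedom out of 80. No new data are needed: GCS is required for eligibility, and age is required for eligibility and already compared at baseline.

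### The DTI mixed model has no tract fixed effect, so differences common to all patients among the 18 tracts are absorbed as patient-by-tract variance; the treatment standard error may be too wide, depending on variances the documents do not give

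*SAP*

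**What the plan says.** In the SAP, under Statistical Analysis, the DTI model has "treatment (light therapy vs. sham) and time point (acute, early sub-acute, late sub-acute) as fixed effects", with "tract and time point nested within each patient as random effects". No fixed tract term is listed, and neither is a tract effect shared across patients. The SAP gives no model formula.

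The measurements are pooled "across treatment groups and three time points, as well as across all 18 tracts". The SAP says the model accounts for "repeated measurements, within-tract and within-subject correlations, and missing time points". On the analysis set it says: "All patients with at least one MRI were included in this analysis".

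The model for clinical symptoms is described separately, with "treatment group and time point as fixed effects, and patient as a random effect".

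Protocol section 9 (Statistical Methods) calls the DTI outcome the primary hypothesis. It sizes the trial as a plain two-group comparison of fractional anisotropy (FA), with one coefficient of variation (CV) of 40% and an assumed effect of 25%.

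**The concern.** The same 18 tracts are measured in every patient, so tract is crossed with patient. A random tract effect within patient is reasonable for a patient's own departures from the usual tract pattern. It does not describe the pattern itself, which all patients share and which belongs in the fixed part of the model. Left out, that pattern has to go somewhere, and the patient-by-tract component takes it. The component then says that a patient's average over 18 tracts is much less certain than it is.

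If the inflation reaches the treatment standard error, the confidence interval for the DTI effect is wider than the data warrant and a real difference is harder to detect. This is the model behind the trial's DTI conclusion.

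**Working it through.** **The plan's own figure.** Section 9 of the protocol gives 41 per group. The rule 16 × CV² / (proportionate change)² gives 16 × 0.40² / 0.25² = 40.96, so 41 per group and 82 in all. (The protocol states neither power nor sidedness; 80% and two-sided are assumed, and they reproduce 41.) The figure stands. It uses one undivided CV, so it does not say how much variation lies between patients and how much between tracts.

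**Where the tract pattern goes.** Take complete data: 18 tracts, 3 time points. Let the SDs be p (patient), k (patient-by-tract), s (patient-by-time point) and e (residual), and let t be the SD of the 18 tract means. Expected mean squares without a fixed tract term:

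- Patient: 54p² + 3k² + 18s² + e²
- Patient-by-tract: 3k² + e² **+ 3t²**
- Patient-by-time point: 18s² + e²
- Residual: e²

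The tract pattern does not enter the patient mean square, because each patient's mean covers the same 18 tracts. It does enter the patient-by-tract mean square.

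**Effect on the patient variance.** The estimate is (patient − patient-by-tract − patient-by-time point + residual) / 54. Its expectation is p² − 3t²/54 = p² − t²/18. While this is positive, the excess in one component is offset exactly by the shortfall in the other, and the treatment standard error does not change. The offset fails when t²/18 > p², that is, when t/p > √18 = 4.24.

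**Check below the threshold.** A REML fit to simulated data with about 25% of sessions missing used t = 0.08 and p = 0.02 on the FA scale (ratio 4).

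| | Without tract term | With tract term |
|---|---|---|
| Patient-by-tract variance | 0.0067 | 0.00022 |
| Patient variance | 0.00010 | 0.00046 |
| Treatment SE | 0.00496 | 0.00496 |

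The arithmetic agrees: 0.08² + 0.00022 = 0.0066, and 0.00046 − 0.08²/18 = 0.00046 − 0.00036 = 0.00010.

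**Size above the threshold.** The correct variance of a patient's mean is p² + k²/18 + s²/3 + e²/54. Once the patient variance is held at zero, the model in effect uses t²/18 in place of p². Assumed SDs, in % of mean FA: k = 5, s = 2, e = 4. The last three terms sum to 1.389 + 1.333 + 0.296 = 3.02.

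| t | p | t/p | Correct | Model | SE ratio |
|---|---|---|---|---|---|
| 25 | 8 | 3.1 | 67.02 | 67.02 | 1.00 |
| 25 | 5 | 5.0 | 28.02 | 34.72 + 3.02 = 37.74 | √(37.74/28.02) = 1.16 |
| 15 | 3 | 5.0 | 12.02 | 12.50 + 3.02 = 15.52 | √(15.52/12.02) = 1.14 |
| 25 | 3 | 8.3 | 12.02 | 37.74 | √(37.74/12.02) = 1.77 |

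Balanced REML simulations of the same settings gave 1.00, 1.15 to 1.18, 1.15, and 1.74 to 1.79. A second set of assumed SDs gave 1.00 to 1.03 at ratio 4, 1.37 to 1.48 at ratio 6 and 1.52 to 1.68 at ratio 8.

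**The case against.** The strongest reply is that the harm is confined to one region. Tract means cancel from the treatment contrast, and below a ratio of about 4.24 nothing happens to its standard error. That is correct, and it limits the point. If the protocol's 40% CV were a between-patient SD, the between-tract SD would have to exceed 4.24 × 40% = 170% of mean FA before any widening. But section 9 takes its starting CV from a cohort measured in 16 brain regions and does not say it is a between-patient figure. It therefore settles the matter neither way.

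A reader might also infer several stronger things that the documents do not support:

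- **A large loss of power.** The protocol's target effect is 25%. With 41 per group and the worst assumed case above, the widened standard error is √(2 × 37.74/41) = 1.36% of mean FA. The effect is then 25/1.36, about 18 standard errors. A marked loss of power appears only if a far smaller effect is supposed, and the plan names none.
- **Standard errors too small because no patient intercept is fitted.** The SAP nests within patient and claims to account for within-subject correlation. Naming patient outright only in the clinical model is loose wording, not evidence of omission.
- **A missing scan effect that inflates a treatment-by-time test.** The SAP names time point within patient as a random effect, and it lists no treatment-by-time term.
- **Imbalance from missing tracts.** The SAP speaks of missing time points and MRI sequences. A missed diffusion scan removes all 18 tracts together.

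**Conclusion.** The model is misspecified as described: a pattern shared by all patients is treated as random variation within each. The inflated patient-by-tract component follows from the text. A wrong treatment standard error does not follow automatically, and it would be too strong to say that the error bars are wrong.

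With all 18 tracts in each scan and a patient intercept, the treatment standard error is right up to a between-tract to between-patient SD ratio of about 4.24. Beyond that it is too wide, by about 1.15 times at ratio 5 and about 1.75 times at ratio 8 under the assumed SDs. The error is conservative for the treatment test. The documents report no variance components, so the side of the threshold on which this trial lies is unknown. The change is worth making because it removes the risk at almost no cost.

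**What to change.** Add tract as a fixed effect and state the model in full: DTI parameter ~ treatment + time point + tract, with random intercepts for patient, patient-by-tract and patient-by-time point. Include treatment-by-time point only if it is to be tested, and say so. Report the estimated variance components, so that a reader can see whether any has been set to zero.

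The SAP is written in the past tense, so in practice this means re-fitting the existing data and disclosing the exact model. The cost is 17 degrees of freedom and a line of code. With 82 patients, 18 tracts and 3 time points there would be up to 82 × 18 × 3 = 4,428 observations. In complete data below the threshold, the treatment result will not change.

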Pregnancy Test b	X		X
Investigational LLLT using the Photomedex		X	

Helmet			
Neuroimaging using Magnetic Resonance		X	X
Clinical Outcomes Assessment		X	X
AE, SAE, UADE Assessment		X	X

a If the subject regains capacity they will be re-consented at the time of follow up.

b Exclusion criteria (E4.) specific for female subjects of childbearing age.

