### 7.2. *Magnetic Resonance Imaging*

Following the 1st Photomedex helmet application, a baseline MRI will be performed, at the earliest opportunity, as soon as the subject is able to lay flat for 1 hour and the scanner is available for use. If the subject is admitted as an inpatient the scan will take place at Lunder 6 on the MGH Main Campus. If the subject is discharged from ED Observation prior to the first MRI, then the baseline MRI will take place at the Martinos Center at the Charlestown Campus. It is anticipated that the MRI will take place within 24-48h hours after enrollment and the scanning protocols themselves will take approximately 60 minutes to perform. Taking into account any necessary set up time before, during and after scanning the total time for the MRI will be approximately 60-90 minutes. If the subject is unable to undergo research-related imaging, this will be deferred until it is safe and feasible. This baseline MRI is performed

following the first application of light therapy because of the need to deliver light therapy as soon as possible after injury, and the clinical challenges of performing MRI within the first 12 hours. A designated study staff member will be responsible for gathering post-procedure follow-up data on the subject. The subjects will be followed until discharge.

Imaging protocol (for baseline and post-treatment imaging):

Subjects will be asked to lie still in a supine position for the duration of the imaging session. Head motion will be minimized during image acquisition by the use of a dedicated head coil with holder.

The MRI protocol may include the following sequences:

- 1) Localizer/Auto-aligned scout
- 2) High resolution T2 weighted imaging
- 3) FLAIR (Fluid attenuated inversion recovery) imaging
- 4) High resolution 3D T1 weighted isotropic imaging
- 5) Susceptibility-weighted imaging (SWI)
- 6) Diffusion tensor imaging (60 encoding directions)
- 7) BOLD EPI functional MRI for the evaluation of resting state functional connectivity (FC) within and between motor, visual, auditory, dorsal attention, executive control, salience and default mode networks.
- 8) Arterial Spin Labeling (ASL) brain perfusion imaging.

No contrast agent or other pharmacological substance other than ones clinically required for the subject will be given.

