## **11. Risk Benefit Analysis**

### **11.1. *Known and Anticipated Risks***

We anticipate the risk to the subjects due to participation in this study to be low. Subjects who have satisfied the inclusion/exclusion criteria as outlined in the protocol will be eligible for enrollment. All subjects will be treated according to the standard of care guidelines for their condition according to the medical staff. For the experimental portion of the procedure, after consent has been obtained, subjects will undergo approximately 20 minutes of exposure to the Photomedex Helmet for at least 2 time points and up to 3 time points. The first helmet application will take place in the inpatient unit or in the ED observation unit. If the subject is admitted as an inpatient he/she may have up to 2 additional helmet applications no sooner than 12 hours after the previous helmet application. If the subject is discharged from either the inpatient unit or the ED observation unit prior to his/her 2nd helmet application, he/she will have up to 2 additional helmet applications no sooner than 12 hours after the previous helmet application arranged either through a follow up visit.

In order to optimize the LLLT, we would like to shave the head. This will be optional to the surrogate/subject and will be explained at the time of informed consent. There is a slight potential risk of a small cut to the head during shaving of the head. In addition, there is a small amount of radiant heat that is generated by the Photomedex helmet. The helmet will be efficiently cooled with fans but depending on the skin and hair color of the subject the temperature of the scalp may be raised enough to be perceived as warmth. In addition, the subject's core temperature will be monitored and in the unlikely event that the temperature increases more than 0.5 C the helmet will be removed.

Following initial exposure to the Photomedex Helmet, a baseline MRI will be performed at the earliest opportunity as soon as the patient is able to lay flat for 1 hour and the scanner is available for scheduling. If the subject is admitted to an inpatient unit, he/she will have the first MRI scan in Lunder 6 at the MGH Main Campus. If the subject is discharged from the ED Observation unit, he/she will have the first MRI scan at the Martinos Center in Charlestown.

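### The SAP's assurance that a baseline DTI difference between arms cannot confound the mixed model is unsupported, and false for the treatment main effect

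*SAP*

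**What the plan says.** The SAP fits the diffusion parameters with "treatment (light therapy vs. sham) and time point (acute, early sub-acute, late sub-acute) as fixed effects", plus random effects for tract and time point within patient. It gives two properties of the model as strengths: "the LME model treats each timepoint as a separate variable", and "it can accommodate data from subjects with missing timepoints". From the first it infers that "any baseline difference in DTI parameters across the LLLT and sham groups did not confound the overall analysis".

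The SAP writes no treatment-by-time interaction, no baseline DTI covariate and no change outcome. P values come from a type III table, but the SAP does not say which term carries the treatment conclusion.

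Protocol section 7.2 says: "Following the 1st Photomedex helmet application, a baseline MRI will be performed". Section 11.1 agrees: "Following initial exposure to the Photomedex Helmet, a baseline MRI will be performed at the earliest opportunity". In the section 7 assessment table, the row "Neuroimaging using Magnetic Resonance" is marked under procedure and follow-up, not under pre-procedure. The row "Clinical Outcomes Assessment" is marked the same way. Section 7.1 allows further applications from 12 hours after the previous one, and section 7.2 expects the scan 24 to 48 hours after enrollment. More than one application may therefore precede the scan called baseline.

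**The concern.** Coding time as levels removes mean changes that both arms share. It does not remove a difference between the arms. Random effects describe variance and correlation, and tolerance of missing scans is a separate matter; neither takes out an arm-level offset.

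A reader who sees the arms differ at the acute scan is told to disregard it, when a persistent difference of that kind would be part of the reported treatment effect. The safety endpoint is unaffected, and the protocol synopsis lists MRI response as secondary. But protocol section 9 sizes the trial on DTI and treats it there as the primary hypothesis, so the reading of the DTI comparison matters.

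**Working it through.** **Inputs.** From the documents: 41 per arm, effect size 25%, CV of fractional anisotropy (FA) 40% (protocol section 9); 18 tracts and three time points (SAP). Assumed, because not given: the correlation rho between scans of a patient's tract mean, taken as equal for all pairs of scans, and the variance split. Units are SDs of the scan mean.

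**1. The plan's own figure.** The rule of thumb 16 × (CV / effect)² gives 16 × (0.40 / 0.25)² = 40.96, so 41 per arm and 82 in total. This matches section 9 (80% power, two-sided 5%, assumed). The planned effect is 0.25 / 0.40 = 0.625 SD.

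**2. Algebra.** Let the arms differ by c before treatment, with c persisting, and let the true effect at scan k be d_k.
- Arm difference at scan k: c + d_k.
- Treatment main effect (average over three scans): c + mean(d_k). The offset enters in full.
- Change from the acute scan: (c + d_3) − (c + d_1) = d_3 − d_1. The offset cancels, and so does any effect already present at the acute scan.

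**3. Pass-through with the SAP's random effects.** Simulation with c = 0.30, no treatment effect, 41 per arm, 18 tracts, scan-mean variance 1, tract and residual variance 0.5 each, generalised least squares with known variance components, 2,000 data sets per cell. Missing 10 / 25 / 40% at the three scans leaves 82 × (0.90 + 0.75 + 0.60) ≈ 185 of 246 scans.

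| rho | Scans | Additive model | Main effect, interaction model |
|---|---|---|---|
| 0.5 | complete | 0.293 | 0.293 |
| 0.5 | missing | 0.299 | 0.299 |
| 0.8 | complete | 0.297 | 0.297 |
| 0.8 | missing | 0.303 | 0.303 |

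The interaction test rejected in 4.6% to 5.8% of the same data sets. A REML fit at rho 0.8 with missing scans (40 data sets) gave 0.295 for both forms.

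**4. How likely such an offset is by chance.** The SD of the persistent arm difference is sqrt(rho × 2/41). The standard error of the overall contrast is sqrt(((1 + 2 rho)/3) × 2/41), compared with a critical t of 1.99 on 80 df.

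| rho | SD of offset | Chance that offset exceeds 0.30 | 0.30 / SE | Rejection at exactly 0.30 |
|---|---|---|---|---|
| 0.2 | 0.099 | 0.2% | 1.99 | 50% |
| 0.5 | 0.156 | 5.5% | 1.66 | 27% |
| 0.8 | 0.198 | 12.9% | 1.46 | 5% |
| 0.9 | 0.210 | 15.2% | 1.41 | 1% |

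Unconditional rejection was 5% for the overall, change and interaction tests. Among the 7% of null trials with an acute difference above 0.4 SD, the overall contrast rejected 27 / 38 / 53 / 60% across these rho values. At rho = 0 it already rejects 20%, because the acute scan is one third of the contrast. The early sub-acute difference alone, which isolates carry-over, rejected 7 / 16 / 37 / 48%, against 5% at rho = 0.

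**5. What the missing pre-treatment scan costs.** At rho 0.7, an observed pre-treatment difference of 0.30 SD biases the main effect by 0.7 × 0.30 = 0.21 SD. Adjusting for a pre-treatment DTI value would bring the bias to about zero and conditional rejection to about 5%, but no such scan is planned. The change contrast is no substitute: for a 0.625 SD effect complete at the acute scan and sustained, it rejects 5% of the time, against 88% for the main effect.

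**The case against.** The strongest reply is randomisation. Protocol section 7 allocates 1:1, so a pre-treatment difference is chance rather than systematic confounding; the main effect is unbiased over randomisations and its type I error is 5%. That stands. But the SAP sentence concerns a difference that is present, and it credits the model, not randomisation. Conditional on such a difference, the estimate is biased.

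Second, the conclusion may rest on a treatment-by-time term, from which a constant offset does cancel. The type III table may hint at one, but none is written, and the sentence covers the whole analysis rather than one contrast. Had an interaction been fitted, the main effect beside it would still carry the offset.

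Third, a difference at the acute scan may be partly early effect, which belongs in the overall contrast. That is true, and the planned data cannot tell the two apart. Section 7.2 openly gives treatment urgency and the difficulty of early MRI as the reasons for the timing. The timing is therefore a disclosed design limit, not an SAP error, and an SAP edit cannot remove it. Section 11.2 mentions routine clinical MRI, but no pre-treatment research DTI is planned.

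Fourth, the pass-through is close to an identity, and the probabilities depend on an assumed rho. At high rho, where offsets above 0.30 SD are most common, an offset of exactly 0.30 rarely produces significance. This is right: the damage is mainly to the estimate.

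**Conclusion.** The inference is unsupported, and for the treatment main effect it is false: a persistent offset passes through one for one, whatever the coding of time, the random effects or the pattern of missing scans simulated. For a change or treatment-by-time contrast a constant offset does cancel, but the SAP does not say that such a contrast was used.

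At 41 per arm, a chance offset above 0.30 SD occurs in 0.2% to 15% of trials for rho from 0.2 to 0.9. These figures rest on equal between-scan correlation and the planned sample size; the number of patients analysed is not given. Overall type I error is intact and the documents show no actual imbalance. The SAP should be corrected because it claims a property the model lacks, which limits what the DTI comparison can support.

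**What to change.** - Withdraw the sentence that a baseline difference did not confound the analysis.
- State whether treatment-by-time was fitted and which term or contrast was tested.
- Label the acute scan as post-first-application, report how many applications preceded it, and state as a limitation that no pre-treatment research DTI was planned.
- Keep the overall treatment contrast. Beside it, report a sensitivity analysis adjusted for pre-treatment variables already collected, such as age and admission GCS. RPQ should not be used: the assessment table does not show clinical outcomes as measured before treatment.
- Report per-scan and change-from-acute contrasts descriptively.
- Label as post hoc anything added after the analysis.

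The cost is rewording and a refit, with no new data. The extra contrasts bring some multiplicity, so they should stay descriptive. The change contrast has almost no power for an effect already complete at the acute scan and must not replace the overall contrast. Covariate adjustment helps only as far as the covariates predict DTI: if they explain 10 / 30 / 50% of the persistent patient variance (assumed), the typical chance offset shrinks by the factor sqrt(1 − R²), to 0.95 / 0.84 / 0.71 of its size.
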